3.4.4 Continuous outcomes

Continuous outcomes will be analyzed using a linear regression model including health system, prior MOUD exposure, and treatment assignment as predictors. The linear regression model is given by:

$$y_{ij} = \alpha_j + \nu P_{ij} + \beta T_{ij} + e_{ij}$$

where α_j are clinic-level fixed effects, β is the effect of CC-COD over EUC, and e_{ij} is an independent and identically distributed mean zero error term. The statistical hypotheses from the linear regressions will be of the form:

$$H_0: \beta = 0 \text{ vs}$$

$$H_1: \beta \neq 0.$$

If necessary, outcomes that require elements from the 6-month follow-up survey may be weighted to account for nonresponse as previously described. Again, if we do not have sufficient sample size to support modeling P_{ij} (prior MOUD treatment), then it will be removed from a given model. We will assess this for each continuous outcome by examining if we have at least 30 individuals with and without prior MOUD treatment in our analytic sample.

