Note that we will not administer item 9 from the PHQ-9 ("thoughts that you would be better off dead, or of hurting yourself") during eligibility screening. This avoids asking for information that could require us to break confidentiality before a participant has completed the informed consent process. It does not affect our eligibility criteria because the 8-item and 9-item versions of the PHQ are scored identically.²⁰⁹ We will obtain a complete initial PHQ-9 score during the baseline interview in one of two ways: (1) if 3 or fewer days pass since the eligibility screener, administer PHQ item 9 during the baseline interview, then combine it with items 1-8 from the eligibility screener for scoring; or (b) if more than 3 days have passed since the eligibility screener, re-administer the full PHQ-9 during the baseline interview and use that full score for all subsequent analyses (this latter option does not affect the eligibility determination).

Patients who screen eligible will be contacted within 4 weeks to participate in the study. The research assistant (RA), who is employed by the RAND/UNM research team, will contact the participant to schedule a study visit that will consist of a screening questionnaire, the informed consent process and a baseline interview assessment. Due to COVID-19, the consent may or may not be conducted in person. We have created a contingency plan based on recommendations from institutional revisions to research procedures. If the consent process will not be conducted in person, the RA will consent the participant via an IRB approved, virtual method: verbal consent with electronic documentation of the consent process. Regardless of whether or not the consent is obtained via telephone or a video conferencing platform, this should not impact the RA's ability to move directly into the baseline assessment immediately following the consent. The participant will be notified ahead of time that they should plan on spending approximately 1 hour to complete this study visit.

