Our revised outcomes are as follows: (1) Buprenorphine continuity of care,⁴ which refers to the numbers of cumulative days the patient receives buprenorphine during the 180 days after study enrollment; (2) Buprenorphine access,⁵ defined as number of days until first buprenorphine prescription after study enrollment, among patients with a new episode of OUD care (i.e., no care for at least 30 days prior); (3) MDD symptom severity, as measured by the PHQ-9²; and (4) PTSD symptom severity, as measured by the PCL-5.¹⁷⁹ Buprenorphine continuity and access will be based on prescription (data and frequency) data from the follow-up assessments and New Mexico and California Prescription Drug Monitoring Program data. MDD and PTSD symptom severity will be collected in baseline and follow-up assessments, with primary outcome analyses based on final scores across the six-month period.

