2.5 Definitions of outcomes

2.5.1 Primary outcomes

Table 1 defines the primary outcomes of this study. The hypotheses associated with these outcomes are as follows:

1. We hypothesize that patients with a new OUD episode of care who are randomized to CC-COD/CC-COD+ will receive buprenorphine within fewer days after that care episode

than new OUD patients who are randomized to enhanced usual care. Alternatively, the null hypothesis is that there will be no difference in the number of days until receipt of buprenorphine with a new OUD episode of care.

2. We hypothesize that patients who are randomized to CC-COD/CC-COD+ will have more days of buprenorphine treatment within 180 days of study enrollment than patients who are randomized to enhanced usual care. Alternatively, the null hypothesis is that there will be no difference in the number of days of cumulative buprenorphine treatment within 180 days of study enrollment.
3. We hypothesize that, among patients with probable depression at study enrollment, those who are randomized to CC-COD/CC-COD+ will have a greater reduction in depression symptoms 6 months after study enrollment compared to those who are randomized to enhanced usual care. Alternatively, the null hypothesis is that there will be no difference in depression symptoms 6 months after study enrollment among those with probable depression at enrollment.
4. We hypothesize that, among patients with probable PTSD at study enrollment, those who are randomized to CC-COD/CC-COD+ will have a greater reduction in PTSD symptoms 6 months after study enrollment compared to those who are randomized to enhanced usual care. Alternatively, the null hypothesis is that there will be no difference in PTSD symptoms 6 months after study enrollment among those with probable PTSD at enrollment.

A union-intersection test will be used to test the overall success of the study that combines the four primary outcomes into a single composite hypothesis. In particular, the null hypothesis is the intersection of the four primary outcome null hypotheses (i.e., all null hypotheses are true), and the alternative is the union of the alternative hypotheses (i.e., at least one alternative hypothesis is true). As described in subsequent sections, either a Bonferroni or Benjamini-Hochberg correction on the individual hypotheses will be used to control the error rate of this composite test.

Table 1: Definition of primary outcomes

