Outcome	Population ^a	Definition	Measure Scale	Source
Buprenorphine access	Study participants with a new episode of OUD care (no care for at least 30 days prior)	Number of days until first buprenorphine prescription after study enrollment	Time-to-event	Survey, PMP
Buprenorphine continuity of care	Study participants not on methadone at baseline	The cumulative number of days the patient receives buprenorphine during the 180 days after study enrollment.	Continuous	Survey, PMP
MDD symptom severity	Study participants with probable MDD at baseline (PHQ-8 \geq 10)	PHQ-9 at 6 months	Sum of items (0-27)	Survey
PTSD symptom severity	Study participants with probable PTSD at baseline (PC-PTSD-5 \geq 3)	PCL-5 at 6 months	Sum of items (0-80)	Survey

^a Study participants means all study participants who consented and were randomized to the intervention or to EUC.

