2.6 Study design

This study is a stratified randomized trial testing CC-COD versus EUC, with strata defined by prior MOUD exposure and primary care clinic.

As part of the CR, we initially planned to compare CC-COD+ to CC-COD, with MOUD continuity of care as the primary outcome. However, despite sustained and targeted efforts, recruitment was lower than expected, and we did not reach our targeted enrollment goals for either CC-COD or CC-COD+. Based on input from our research advisory board and NIH project officer, we now plan to combine the CC-COD and CC-COD+ samples when analyzing the data for additional information about the potential effectiveness of the intervention. Since the Collaborative Care Model is identical across both trials, and the only difference between the arms is in the additional clinical modules supported by CC-COD+, combining the active CC-COD and CC-COD+ arms for an exploratory analysis should provide additional precision around the estimated treatment effect for CC-COD/CC-COD+.

The study's original target sample size was 900, with an additional 300 patients targeted for the CR, for a combined target of 1200. Our final sample size was 797 (729 following the original protocol and 68 following the protocol from the CR). This analysis plan has been modified to include actual final power calculations calculated prior to breaking the blind but after all data collection ended.

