3.3 Baseline Characteristics

We will conduct descriptive analyses comparing CC-COD/CC-COD+ and EUC characteristics at baseline using a Chi-squared test for categorical variables and a two sample t-test otherwise. Table 6 provides the demographic characteristics of the study participants at baseline. Table 7 provides all outcomes at baseline and at the 6-month follow-up.

Table 6: Sociodemographics and other covariates at baseline

	Overall	Treatment Assignment	
		CC-COD	EUC
Age, n (%)			
18-30 years			
31-40 years			
41-50 years			
51 years and older			
Sex, n (%)			
Male			
Female			
Gender-neutral sex designation (X)			
Race/Ethnicity, n (%)			
White, Non-Hispanic			
Hispanic			
Other race, Non-Hispanic			
Education, n (%)			
Less than high school diploma			
High school graduate/GED			
Any college/higher-level education			
Marital Status, n (%)			
Never Married			
Married/Partnered			
Divorced/Separated/Widowed			
Prior MOUD, n (%)			
Health system, n (%)			
Health system 1			
...			
Health system 4			

Table 7: Outcomes at baseline and 6-months

	Baseline			6-Months		
	Overall	CC-COD	EUC	Overall	CC-COD	EUC
Primary outcomes						
Buprenorphine access, mean (SD) ¹						
Buprenorphine continuity of care, mean (SD)						
PTSD, n (%)						
PTSD Symptoms, mean (SD)						
MDD, n (%)						
MDD Symptoms, mean (SD)						
Secondary outcomes						
Access to MDD and/or PTSD treatment, n (%)						
Quality of care for MDD, n (%)						
Quality of care for PTSD, n (%)						
MDD remission, n (%)						
MDD response, n (%)						
PTSD remission, n (%)						
PTSD response, n (%)						
Suicidality, n (%)						
Opioid Use Frequency, mean (SD)						
Opioid Overdose Events, n (%)						
Physical Health Functioning, mean (SD)						
Mental Health Functioning, mean (SD)						
Exploratory outcomes						
Drug use frequency, mean (SD)						
Stimulant use frequency, mean (SD)						
Alcohol use, mean (SD)						
Opioid Overdose Risk Behaviors, mean (SD)						
Opioid use severity, mean (SD)						

NOTES: ¹Gray cells indicate outcomes not measured at baseline

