3.5.1 Primary outcomes

We used the observed distributions for our continuous variables including the following: for the planned power calculations were:

1. We observed a mean number of days until accessing Buprenorphine of 26.0 with a standard deviation of 31.9. Our total sample size for this analysis was 137 individuals with 6-month follow-up data.
2. Among those who initiate medication for OUD, the mean number of days of continuous treatment for OUD is 133.0 with a standard deviation is 54.1. The total sample size for this analysis was 392 individuals with 6-month follow-up data.
3. Among those with probable depression at enrollment ($\text{PHQ-8} \geq 10$), the mean depression symptoms score (PHQ-8) at 6 months of 11.5 with a standard deviation of 6.6. The total sample size for this analysis was 405 individuals with 6-month follow-up data.
4. Among those with probable PTSD at enrollment ($\text{PC-PTSD-5} \geq 3$), the mean PTSD symptoms score (PCL-5) at 6 months of 32.2 with a standard deviation of 17.8. The total sample size for this analysis was 368 individuals with 6-month follow-up data.

Under these observed outcome distributions as well as the final number of individuals with observed outcome values in our data, we have 80% power to detect:

1. A hazard ratio of at least 0.45 if we find a protective effect and see fewer days until accessing Buprenorphine. This corresponds to at least a hazard ratio of 2.25 if the direction were reversed or a 27-percentage point difference if the outcome was modeled as a binary measure. Notably, a previous study of Collaborative Care for opioid and alcohol use disorders found a 22-percentage point increase over enhanced usual care so if the effect is large in CLARO, we may be able to detect it.⁸
2. 18.3 additional days of continuous OUD treatment within the first 180 days. A growing body of evidence suggests the mortality is lower during OUD treatment, and that mortality is increased in the first four weeks after treatment cessation.⁹
3. A 2.2 point reduction in depression symptoms (PHQ-8). This provides power to detect effects below the clinically important difference for individual change of 5 points.¹⁰
4. A 6.23 point reduction in PTSD symptoms (PCL-5). A previous study of delivering PTSD treatment in primary care setting to active duty military found a reduction in PTSD symptoms of 7 points.¹¹

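### The two primary symptom models leave out the baseline PHQ-9 and PCL-5 scores that the trial collects, which gives up precision, and the SAP's responder check has no comparison by arm

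*SAP*

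**What the plan says.** SAP 3.4.4 gives the whole model for continuous outcomes: "Continuous outcomes will be analyzed using a linear regression model including health system, prior MOUD exposure, and treatment assignment as predictors". The note to SAP Table 11 repeats the list, with clinic in place of health system and again no baseline score. Protocol 9.4.1 and 9.4.2 leave covariates to the SAP. The SAP does define a vector of baseline characteristics (3.4.1), but uses it only in the non-response model (3.4.2) and the mediation models (3.4.7).

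The baseline scores exist. Protocol 8.1 states that "MDD and PTSD symptom severity will be collected in baseline and follow-up assessments", and SAP 3.3 that "Table 7 provides all outcomes at baseline and at the 6-month follow-up". For the PHQ-9, Protocol 8.1 also fixes how the baseline score is formed. If more than three days have passed since screening, staff "re-administer the full PHQ-9 during the baseline interview and use that full score for all subsequent analyses"; otherwise item 9 is added to the eight screening items.

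Randomisation does not balance on these scores: it is stratified "with strata defined by prior MOUD exposure and primary care clinic". The outcome is the follow-up score (for PTSD, "PCL-5 at 6 months"), while the hypothesis for depression is that intervention patients "will have a greater reduction in depression symptoms 6 months after study enrollment"; the PTSD hypothesis has the same form.

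On non-response, SAP 3.4.2 compares responders with the full baseline sample by effect size for each outcome, and drops weights if most differences are below about 0.1 or 0.2. No comparison by arm is stated.

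**The concern.** The baseline value of a symptom scale is usually among the best predictors of its later value. Two of the four primary endpoints are each tested at 1.25% without it, in a trial that enrolled 797 against a combined target of 1,200. At most 525 of 797 (66%) have 6-month survey data, where 80% was planned. Precision is scarce, and here it can be had from data already in hand.

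The hypotheses speak of reduction while the outcome is a final score. With baseline in the model this no longer matters. If y = a + bT + cx, then y − x = a + bT + (c − 1)x, so the arm coefficient b is the same for the 6-month score and for the change.

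The responder check is a separate, smaller matter. Bias in a treatment contrast comes from responders differing between arms. A check of pooled responders against the full sample can look clean when the two arms drift in opposite directions, and the weights would then be dropped.

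**Working it through.** **Inputs.** SAP 3.4.2, 3.5 and 2.7: two-sided α = 0.0125, 80% power, 1:1 allocation. SAP 3.5.1: depression N = 405, SD 6.6; PTSD N = 368, SD 17.8. (SAP 3.5.1 labels the depression score PHQ-8, while Table 1 defines the outcome as PHQ-9; the SD is used as given.) The correlation r between baseline and 6-month score is **not in the documents** and is assumed.

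**1. Reproduce the SAP's figures.** Detectable effect = (2.498 + 0.842) × SD × 2/√N; the sum is 3.339 before rounding.
- PHQ: 3.339 × 6.6 × 2/√405 = 2.19 (SAP: 2.2)
- PCL-5: 3.339 × 17.8 × 2/√368 = 6.20 (SAP: 6.23)

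The match shows that the SAP's figures use the full SD, with no reduction for baseline.

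**2. Add the baseline score.** The residual SD becomes SD × √(1 − r²). The gain in patients is 1/(1 − r²) − 1. Power at the SAP's own effects is Φ(d / (2 × SD × √(1 − r²)/√N) − 2.498), with d = 2.2 or 6.23.

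| r (assumed) | PHQ detectable | PCL-5 detectable | Power | Equivalent extra patients |
|---|---|---|---|---|
| 0 | 2.19 | 6.20 | 80% | 0% |
| 0.2 | 2.15 | 6.07 | 82% | 4% |
| 0.3 | 2.09 | 5.91 | 85% | 10% |
| 0.4 | 2.01 | 5.68 | 88% | 19% |
| 0.5 | 1.90 | 5.37 | 92% | 33% |
| 0.6 | 1.75 | 4.96 | 95.5% | 56% |

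**3. Allow for restricted entry.** The analysis populations require PHQ-8 ≥ 10 or PC-PTSD-5 ≥ 3, which narrows the baseline spread and lowers r. If the baseline SD is a fraction u of its unrestricted value, r′ = r·u/√(1 − r² + r²u²). For r = 0.5:
- u = 0.6 (assumed): r′ = 0.33, 12% more patients, detectable 2.07 and 5.86
- u = 0.8 (assumed): r′ = 0.42, 21% more patients, detectable 1.99 and 5.63

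**4. Responder check, by simulation.** Settings: 3,000 replicates, no true effect, N = 614 randomised (405/0.659, assuming the overall 525/797 response applies), 65.9% response in each arm, r = 0.3 and 0.5. Slopes are log-odds of response per SD of the score. Effect sizes (ES) compare responders with everyone randomised.

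| Response depends on | Slopes by arm | Overall ES | ES by arm | Bias, unadjusted (SD) | Bias, adjusted (SD) |
|---|---|---|---|---|---|
| baseline | 0.3 / 0.3 | 0.10 | 0.10, 0.10 | 0.00 | 0.00 |
| baseline | 0.3 / 0.1 | 0.07 | 0.10, 0.03 | 0.02–0.03 | 0.00 |
| baseline | +0.3 / −0.3 | 0.00 | 0.10, −0.10 | 0.06–0.10 | 0.00 |
| 6-month score | +0.3 / −0.3 | – | – | 0.20 | 0.18–0.15 |

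In the third row the overall effect size is below 0.1 in at least 99.9% of simulated trials, while the responders in the two arms differ by 0.20 SD at baseline. The bias of 0.06 to 0.10 SD is 0.4 to 0.7 PHQ points (× 6.6) or 1.1 to 1.8 PCL-5 points (× 17.8). In the last row, adjustment removes only about 9% to 24% of the bias.

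**The case against.** The printed model is valid. It is pre-specified, unbiased with complete data, and its power figures reproduce. The detectable effects also lie below the SAP's references of 5 PHQ points and 7 PCL-5 points. All of that stands: this is unused precision, not an error or a failed power claim. The PTSD margin is the narrow one (6.23 against 7).

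The sponsor deliberately moved from change scores to final scores (Protocol 3 and 8.1). That explains the outcome definition, but it is not an argument against adjusting the final score for baseline.

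The gain depends on a correlation that nobody has reported, and at r = 0.2 it is slight. This also stands. The omission is certain; the size of the benefit is not.

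On the responder check, the SAP does not exclude a split by arm, equal and opposite slopes are a constructed case, and the milder 0.3/0.1 pattern gives only 0.02 to 0.03 SD. The weight model printed in SAP 3.4.2 includes arm, and the planned machine learner could fit interactions. Protocol 9.4.2 even states weighted models for both symptom endpoints without condition. These points make this part minor. They do not remove it, because under the SAP weights are used only if the stated check calls for them.

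**Conclusion.** The concern holds. Neither primary symptom model contains the baseline score, both scores are available, and no other section brings them in. The loss is one of precision: 4% to 56% in equivalent patients for assumed correlations of 0.2 to 0.6, with the upper end unlikely if restricted entry lowers the correlation as illustrated. A secondary benefit of adjustment is protection against differential non-response that baseline severity explains. It gives little protection if response depends on the unseen 6-month score.

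With about a third of participants lacking 6-month survey data, differential non-response is possible but not shown, and the simulated patterns are illustrations. The SAP's choice to weight only when needed is not disputed. The change should be made, but the primary analysis is valid without it.

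**What to change.** **Primary models (SAP 3.4.4).** If the blind still holds, add one linear covariate to each model: the baseline PHQ-9 total, formed as Protocol 8.1 describes, for MDD symptom severity; and the baseline PCL-5 total for PTSD symptom severity. Bring the Table 11 note into line. SAP 2.2 says the plan was finalised before unblinding, and data collection has ended. If unblinding has since occurred, keep the printed model as primary and report the adjusted model as a labelled sensitivity analysis.

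**Responder check (SAP 3.4.2).** Report it by arm as well as overall, including the difference in baseline score between the two arms' responders. If weights are then used, state that the learner includes arm and the baseline score and can fit their interaction.

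**Cost.** One degree of freedom per model, one extra table and a few sentences; no new data. SAP 3.4.2 already has rules for missing baseline items. Both scales are sums, so gaps of under half the items are handled by rescaling. Only the rarer fallback imputes a composite using treatment assignment, and that should be looked at again once the score is a primary covariate.

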3.4.5 Survival outcome

Buprenorphine access, the survival outcome that is measured in the PMP and survey will be analyzed using a Cox proportional hazard regression model including health-system, prior MOUD exposure, and treatment assignment as predictors. The Cox proportional regression model is given by:

$$h(t) = h_0(t) * \exp(\alpha_j + \nu P_{ij} + \beta T_{ij})$$

where α_j are health system-level fixed effects, and e^β is the hazard ratio effect of CC-COD over EUC. The statistical hypotheses from the Cox proportional hazard regression will be of the form:

$$H_0: \beta = 0 \text{ vs}$$
$$H_1: \beta \neq 0.$$

Outcomes that are measured as part of the 6-month follow-up survey may be weighted to account for nonresponse as previously described. Again, if we do not have sufficient sample size to support modeling P_{ij} (prior MOUD treatment), then it will be removed from a given model. We will assess this for each continuous outcome by examining if we have at least 30 individuals with and without prior MOUD treatment in our analytic sample. We will right censor all observations for those individuals who did not ever receive buprenorphine during the course of follow-up for these analyses.

3.4.6 Moderation analyses

All analyses of subgroups are considered exploratory. We will explore the data to understand if any of the following baseline factors moderate the effect of the intervention:

- Sex
- Ethnicity
- Stimulant use (methamphetamine or cocaine use)
- Housing status
- History of trauma/interpersonal violence

- Pain (PEG)
- Disability and impairment (SDS)
- Number of care coordinator visits

Definitions for these moderation variables are described in Table 4. Additional moderators may be explored as warranted. Statistical hypotheses testing whether the effect of the intervention varies by these factors will be tested by the inclusion of an interaction between the moderating factor and the treatment assignment into the previously described models. We will also utilize propensity score weighting if deemed necessary here to correct for potential imbalances between the treatment groups within levels of the moderators.⁵

